Study Objectives	
Primary objective:
 
 • Compare the effectiveness of having the Behavioral Health – Virtual Patient Navigation (BH-VPN) program available compared to usual care, on admission rates among patients in the ED with a telepsychiatric consult 
Secondary objectives:
 
 • Compare demographics and Charlson comorbidity score between the two arms of the study • Compare the patient-centric 45-day utilization rate after the ED visit (ED, IP, OBS, encounter) between the 2 arms of the study • Compare the frequency of patients with an encounter with a self-harm diagnosis within 45 days of the ED visit between the 2 arms of the study • Compare the frequency of patients who return to the ED and have a telepsychiatric consult within 45 days of their initial ED visit between the 2 arms of the study 
Reporting for the Duke Foundation:
 
 • Count/frequency of patients in the intervention and usual care arms presenting to an ED that have a telepsychiatric consult during the intervention • Count/frequency of patients with an admission after telepsychiatric consult in the intervention arm • Count/frequency of patients active in the BH-VPN • Count/frequency of patients active in the BH-VPN program that had an encounter with a self-harm code within 45 days of their ED visit • Count/frequency of patients active in the BH-VPN program that have an acute care visit (ED, IP, OBS) within 45 days of their ED visit • Count/frequency of patients active in the BH-VPN program that return to an Atrium Health emergency department with a telepsychiatric consult within 45 days of their ED visit • Count/frequency of patients active in the BH-VPN program that improve their PHQ-9 score, among patients with an initial score >10

	
 • Count/frequency of active in the BH-VPN program that report suicide ideation on their initial PHQ-9 (Q2>0), that no longer report suicide ideation on their last PHQ-9 (Q2=0) • Count/frequency of patients active in the BH-VPN program with successful case closure (complete the program or have a successful referral in care)

Inclusion/ Exclusion Criteria
	
Inclusion:
 
 • Present to an ED at participating sites • Complete a telepsychiatric consult as captured in the electronic medical record • Complete a telepsychiatric consult during the navigator’s hours of operation • ≥ 18 years of age at time of ED encounter 
Exclusion:
 
 • No exclusions

Study Procedures
	
Patients are identified by a clinician in the ED as needing psychiatric evaluation and a referral is made to a tele-psych provider for a virtual consult. Patients who complete a telepsychiatric consult in the ED can be enrolled to either the control or intervention arm based on a randomization scheme that randomly allocates days that navigators are available. Psychiatrists are reminded through daily communication as to whether the BH-VPN program is available and the ED locations. The psychiatrist will make a recommendation to admit or discharge the patient. For patients that have a discharge recommendation on days that BH-VPN is available, patients will be offered the BH-VPN program. Enrolled patients are followed for up to 45 days. Each patient will receive the following core components:
 
 1. Introduction to the patient follow-up process prior to discharge 2. Follow-up evaluation within 72 hours by phone and weekly contact 3. Confirm that an in-person follow-up visit with an appropriate provider or clinician is scheduled. Where applicable, confirm in-network follow-up appointments are completed. 4. Ongoing assessment: substance use disorder, medication barriers, and appointment barriers 5. Assist with community resources, crisis planning, and supportive listening 6. Placement into an appropriate case management program, if needed. 
On days where the navigator is available, all patients who meet eligibility criteria will be considered exposed to the intervention; whereas, on days the navigator is not available all patients will be considered exposed to usual care.

Statistical Analysis	Analyses will include all patients identified as having completed telepsychiatric consult and meeting the inclusion criteria. Baseline comparisons of the intervention and usual care groups will be made using univariate analyses. The primary outcome, hospital admission, and secondary outcomes will be compared between the two groups of patients using generalized linear mixed-effects model with a logit link function. Results will be presented with odds ratios and 95% confidence intervals.
-----------------------------	--

LIST OF ABBREVIATIONS

BH-VPN	Behavioral Health - Virtual Patient Navigation
CORE	Center for Outcomes Research and Evaluation
C-SSRS	Columbia – Suicide Severity Rating Scale
DHHS	Department of Health and Human Services
EHR	Electronic Health Record
ED	Emergency Department
EDW	Enterprise Data Warehouse
FY	Fiscal Year
NC	North Carolina
OCTR	Office of Clinical and Translational Research
PHI	Private Health Information
SOP	Standard Operating Procedures

TABLE OF CONTENTS

1.1.	Hypothesis.....	8
1.2.	Primary Objective.....	8
1.3.	Secondary Objectives.....	8
1.4.	Reporting for the Duke Foundation.....	8
2.	BACKGROUND.....	9
3.	RATIONALE.....	10
4.	SUBJECT AND SITE SELECTION.....	10
4.1.	Accrual.....	10
4.2.	Eligibility Criteria.....	11
4.2.1.	Inclusion Criteria.....	11
4.2.2.	Exclusion Criteria.....	11
4.3.	Evaluable Population.....	11
5.	OVERALL DESIGN.....	11
5.1.	Outcome Variables.....	11
5.1.1.	Primary Outcome Variable.....	11
5.1.2.	Rates and Variable Descriptions.....	11
5.1.3.	Reporting for the Duke Foundation.....	12
5.2.	Randomization and Allocation.....	12
5.3.	Behavioral Health Virtual Patient Navigation (BH-VPN) Program.....	13
5.4.	Follow-up.....	14
5.5.	Patient Graduation from the BH-VPN Program.....	14
5.6.	Continuation of the Intervention.....	14
6.	DATA COLLECTION AND REPORTING.....	14
6.1.	Sample size analysis and statistical analysis.....	15
6.2.	Statistical analysis.....	15
6.3.	Data Collection Dates.....	16
7.	INTERVENTION PLAN.....	16
7.1.	Navigator Assessments.....	16
7.2.	Follow-up Assessments.....	16
8.	STUDY GOVERNANCE.....	17
8.1.	Protocol and Pathway Training.....	17

9. SAFETY RISKS AND REPORTING	17
9.1. Data Quality Assurance	18
9.2. Data Monitoring by the Sponsor	18
10. RESEARCH COMPLETION	18
11. ETHICAL AND LEGAL ISSUES	19
11.1. Ethical and Legal Conduct of the Study	19
11.2. Confidentiality	19
11.3. Disclosure of Data	19
12. RETENTION OF RECORDS	20
13. PUBLICATION POLICY	20
REFERENCES	21

1.1. Hypothesis

Index admission rates will be lower among patients who complete a tele-psych consult at an ED on days where the Behavioral Health - Virtual Patient Navigation (BH-VPN) program is available compared to patients who complete a tele-psych consult at an ED on days where the BH-VPN program is not available.

1.2. Primary Objective

Compare the effectiveness of having the VBHI program available compared to usual care, on modifying the admission rate from the ED.

1.3. Secondary Objectives

The secondary objectives are to compare the behavioral health – virtual patient navigation team’s effect on additional patient outcomes

- I. Compare the patient-centric 45-day utilization rate after the ED visit (ED, IP, OBS, encounter)
- II. Compare the frequency of patients with an encounter with a self-harm diagnosis within 45 days of the ED visit
- III. Compare the frequency of patients who return to the ED and have a telepsychiatric consult within 45 days of their initial ED visit

1.4. Reporting for the Duke Foundation

- Count/frequency of patients presenting to an ED that have a telepsychiatric consult during the intervention
- Count/frequency of patients with an admission after telepsychiatric consult in the intervention arm
- Count/frequency of patients enrolled in the BH-VPN program
- Count/frequency of patients enrolled in the BH-VPN program that had an encounter with a self-harm code within 45 days of their ED visit
- Count/frequency of patients enrolled in the BH-VPN program that have an acute care visit (ED, IP, OBS) within 45 days of their ED visit
- Count/frequency of patients enrolled in the BH-VPN program that return to an Atrium Health emergency department with a telepsychiatric consult within 45 days of their ED visit
- Count/frequency of patients enrolled in the BH-VPN program that improve their PHQ-9 score, among patients with an initial score >10
- Count/frequency of patients enrolled in the BH-VPN program that report suicide ideation on their initial PHQ-9 (Q2>0), that no longer report suicide ideation on their last PHQ-9 (Q2=0)

- Count/frequency of patients enrolled in the BH-VPN program with successful case closure (complete the 45-day follow-up period or have a successful referral in care)

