5.1.3. Reporting for the Duke Foundation

- Count/frequency of patients presenting to an ED that have a telepsychiatric consult during the intervention
- Count/frequency of patients with an admission after telepsychiatric consult in the intervention arm
- Count/frequency of patients enrolled in the BH-VPN program
- Count/frequency of patients enrolled in the BH-VPN program that have an encounter with a self-harm code within 45 days of their ED visit
- Count/frequency of patients enrolled in the BH-VPN program that have an acute care visit (ED, IP, OBS) within 45 days of their ED visit
- Count/frequency of patients enrolled in the BH-VPN program that return to an Atrium Health emergency department with a telepsychiatric consult within 45 days of their ED visit

PHQ-9 are taken about every 2 weeks during a patient's enrollment. The post PHQ-9 score will be the score closest to the 45-day follow-up period.

- Count/frequency of patients enrolled in the BH-VPN program that improve their PHQ-9 score, among patients with an initial score >10
- Count/frequency of patients enrolled in the BH-VPN program that report suicide ideation on their initial PHQ-9 ($Q9>0$), that no longer report suicide ideation on their last PHQ-9 ($Q9=0$)
- Count/frequency of patients enrolled in the BH-VPN program with successful case closure (complete the 45-day follow-up period or have a successful referral in care)

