6.2. Statistical analysis

Prior to analysis, descriptive statistics will be calculated to screen all variables for accuracy and to examine distributions.

All analyses will follow the intention-to-treat (“ITT”) principle, such that patients will be analyzed based on their assignment to the BH-VPN program or usual care. Balance in baseline characteristics between the groups will be assessed using Student’s t-test for normally distributed data, the Wilcoxon rank sum test for ordinal data or interval data that are not normally distributed, and the chi-square test for categorical data. Normality will be assessed using the Shapiro Wilk test and Q-Q plots.

The primary outcome, hospital admission (yes/no), is a binary dependent variable and will be compared between the BH-VPN and usual care groups using a generalized linear mixed-effects model with a logit link function. To adjust for correlation among patients seen on the same day and in the same ED, the model will include a random effect term for day nested within ED. The primary predictor in the model is an indicator for assignment to the BH-VPN program versus usual care. Additional baseline covariates will be included in the model if they are either strongly correlated with the dependent variable or show baseline imbalance between the two groups.

A similar approach will be used for the secondary outcomes to assess the patient-centric 45-day utilization rate, encounters with a self-harm diagnosis rate, and ED readmission rate. The models assessing these measures will be generalized linear mixed-effects models with a logit link, where utilization, diagnosis, or readmission, (yes/no) is the binary dependent variable. Independent variables in the models will be as described above for the primary analysis.

In addition, per-protocol analyses of the primary and secondary outcomes will be performed to evaluate the effect of BH-VPN program participation, in contrast to the ITT analysis evaluating the effectiveness of randomization to the program. The per-protocol analyses will include only subjects who received and adhered to the treatment (BH-VPN program or usual care).

Other binary outcome variables (e.g., frequency of patients active in the BH-VPN program) will be analyzed using descriptive statistics, unadjusted odds ratios, and 95% confidence intervals.

All tests will be two sided and the data will be analyzed using SAS Enterprise Guide 7.1 (SAS Institute Inc., Cary, NC, USA).

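### The funder-reported measure of suicide ideation resolving on the PHQ-9 is defined by item Q2 in the synopsis and Section 1.4 but by item Q9 in Section 5.1.3

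*Combined protocol and SAP*

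**What the plan says.** The measure appears three times, each time in the list of results to be reported to the Duke Foundation.

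- **Section 1.4** counts enrolled patients who "report suicide ideation on their initial PHQ-9 (Q2>0), that no longer report suicide ideation on their last PHQ-9 (Q2=0").
- **The synopsis (Study Objectives)** has the same line with the same item, Q2. It counts patients active in the program, where Section 1.4 counts those enrolled.
- **Section 5.1.3**, under Outcome Variables, counts enrolled patients who "report suicide ideation on their initial PHQ-9 ($Q9>0$), that no longer report suicide ideation on their last PHQ-9 ($Q9=0"). The dollar signs come from the reading of the PDF.

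Section 5.1.3 is also the only one of the three with measurement rules. It says that the PHQ-9 is taken about every two weeks, and then: "The post PHQ-9 score will be the score closest to the 45-day follow-up period". Section 6 says that assessment data are stored in HealtheCare, that an application specialist retrieves them, and that an annual report covers the Duke Foundation measures. Section 6.2 says that other binary outcomes "will be analyzed using descriptive statistics, unadjusted odds ratios, and 95% confidence intervals".

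**The concern.** The item number in brackets is the working definition of the result. It decides who counts as having ideation at the start and who counts as free of it at the end. If the number points to another question, the report shows change in some other symptom under the label of resolved suicide ideation.

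All three texts are current, none is an amendment log, and nothing says which one governs. A data request written from the synopsis or Section 1.4 would pull a different field from one written from Section 5.1.3. No other listed result would expose the error. The C-SSRS is given at each phone contact (Section 5.3), but no C-SSRS result is on any reporting list, so this PHQ-9 item is the only ideation result that the plan reports.

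**Working it through.** No sample size, power or event count enters this point, so the check is a comparison of the three texts.

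| Place | Ideation at the start | No ideation at the end | Population |
|---|---|---|---|
| Synopsis | Q2 > 0 | Q2 = 0 | active in the program |
| Section 1.4 | Q2 > 0 | Q2 = 0 | enrolled |
| Section 5.1.3 | Q9 > 0 | Q9 = 0 | enrolled |

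**Step 1: is it the same measure?** Yes. The words that name the construct, the instrument and the two time points are the same in all three places. Only the item number differs, apart from active versus enrolled.

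**Step 2: does the item number change the result?** Write k for the item. The denominator is the number of participants with item k > 0 at the initial PHQ-9. The numerator is the number of those with item k = 0 at the last PHQ-9. Both depend on k:

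- A participant with Q2 > 0 and Q9 = 0 at the start is in the denominator under Q2 and outside it under Q9. The reverse pattern does the opposite.
- A participant with both items above 0 at the start, and with Q2 = 0 but Q9 > 0 at the end, counts as resolved under Q2 and as unresolved under Q9.

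The two definitions agree only if every participant falls on the same side of zero on both items at both times. If the frequency were instead taken over all participants, the denominator would be common to both rules but the numerator would still differ.

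**Step 3: can both be right?** No. They are two numbered items of one questionnaire, and the plan gives each as the single item for ideation. At least one is wrong.

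**Step 4: which one?** The documents do not settle it, because no section lists the PHQ-9 items. Section 5.1.3 is the natural text to follow, since it sits under Outcome Variables and carries the timing rule. Q2 appears twice, including in the synopsis. Neither fact is proof.

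**Step 5: how large is the change?** It cannot be estimated. The documents give no endorsement rate for any PHQ-9 item and no joint distribution of two items. They also do not say what share of patients will accept the program or have a later PHQ-9.

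**The case against.** The strongest reply is that this is a slip in a cross-reference with little consequence. All three versions name the construct in words, so a careful programmer would look for the ideation question whatever the number says, and would probably work from Section 5.1.3. The measure is neither the primary outcome (Section 5.1.1), nor a secondary objective (Section 1.3), nor a variable in Section 5.1.2. It is counted only among program participants, so it has no usual-care counterpart and no between-arm model uses it. Self-harm encounters are compared between the arms separately, and suicide-risk screening by phone uses the C-SSRS.

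Most of this stands, and it limits the weight of the point. It does not remove the point. The plain-language label makes the error easier to catch, but the written rule is still contradictory and no text says that Section 5.1.3 governs. It is also conceivable that the two numbers come from two numbering schemes, such as a local form. The documents do not say so, and all three lines name the PHQ-9 alone.

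A reader might infer more than the documents support in two ways:

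- **That the two Q2 definitions are shown to count another symptom.** That needs the content of the questionnaire, which the documents do not reproduce. They show only that the item numbers conflict.
- **That the shift can be given a number.** One could start from about 566 intervention patients (half of the target of 1,133), apply a discharge rate and assume how often each item is endorsed. The endorsement rates would have no basis in the documents. Patients may also decline navigation (Sections 3 and 5.3), and a PHQ-9 at follow-up is only a possible component (Sections 5.3 and 7.2).

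**Conclusion.** The contradiction is real and needs correcting. One reported measure has two item definitions, and at least one of them would give a wrong numerator and denominator and a mislabeled result. This rests only on the text of the three sections and on Q2 and Q9 being different items of the same questionnaire.

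The reach is narrow: a descriptive count for the funder, among BH-VPN participants only. It would be wrong to infer a threat to the trial's comparative results or to its safety procedures. The admission comparison, the 45-day secondary outcomes, the sample size and the C-SSRS screening do not use this item. The correction is still worth making before the annual report is programmed, because the result concerns suicidality and no other reported ideation measure would show the mistake.

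**What to change.** 1. Check the PHQ-9 form used in HealtheCare and confirm which item records suicide ideation.
2. State that one item in the synopsis, Section 1.4 and Section 5.1.3. If the form confirms Q9, align the synopsis and Section 1.4 to Section 5.1.3.
3. Program the annual Duke Foundation report from that item only, and name the data field in the report specification.
4. In the same edit, use one population term (active or enrolled) in all three places.

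If Q9 is confirmed, the item correction is two changes of wording and one check of the form. If Q2 is confirmed, it is one change, in Section 5.1.3. No new data are needed, and the models and the sample size stay as they are.

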2. BACKGROUND

The primary arena for emergency psychiatric care is in emergency departments (ED), largely because of the impact of deinstitutionalization and other social forces on the mentally ill community.^{1,2} Lack of community-based care for mental illness has contributed to increasing inpatient behavioral health admissions and long stays in the emergency department.³ The high volume of psychiatric patients seen and waiting in hospital EDs may prevent other medical patients from obtaining timely care.⁴ The average delay for admission to a NC state hospital for psychiatric care in 2012 was 3 days and rose to 3.5 days in 2013.⁵ Other contributors to the problem of patients with psychiatric conditions crowding EDs include diminishing access to mental health care in the community, shrinking mental health resources, and increasing fragmentation of resources.⁶

Mental health care in rural regions is a national priority.⁷ In 2016, 18.7% of residents of rural counties have some diagnosed form of mental illness. In addition, 3.9%, or approximately 1.3 million residents of rural counties experienced serious thoughts of suicide.⁸ The Tennessee Hospital Authority estimates a cost of \$9,472 for an inpatient admission with a behavioral health diagnosis.⁹ EDs servicing rural areas often do not have the staff to support patients presenting with a behavioral health crisis. In North Carolina, 70 of its 100 counties have no child and adolescent psychiatrists, 28 have no practicing psychiatrists and 18 counties have only one psychiatrist.¹⁰

Visits to EDs for behavioral health crises are common; in North Carolina, a person in behavioral health crisis presents to an ED every 2.5 minutes.¹¹ Due to the lack of coordinated resources and high recidivism, many patients are admitted to a psychiatric facility perhaps unnecessarily, rather than receiving the care coordination that could prevent an admission.⁶ Virtual care offers an efficient means for patient evaluation, treatment recommendations, and follow-up care due to the remoteness of rural EDs and lower volume of patients needing services. Integrating patient navigation into emergency mental health care delivery may address many of the barriers to patient success post-discharge. Patient navigation has a growing evidence base for improving patient outcomes.¹² The use of virtual care has been shown to improve access and engagement of patients with their care teams. Post-discharge follow-up has also been shown to effectively reduce suicide attempts, with one study that evaluated periodic phone check-in after ED discharge showing a 30% reduction in suicide attempts.¹³

The proposed study builds upon evidence of virtual patient navigation effectiveness among prior research. The novelty of this study is in its design, as prior studies have used cohort designs for causal inference to inform care delivery for patients with mental illness. This randomized trial will provide greater precision and rurality to assess evidence of whether the addition of virtual patient navigation to telepsychiatric consults decreases initial hospitalization, readmissions, and repeated use of the ED among patients presenting to rural EDs with a behavioral health crisis.

3. RATIONALE

To enhance the care of patients with a telepsychiatric consult, Atrium Health has designed a Behavioral Health Virtual Patient Navigation (BH-VPN) program. Navigators will monitor patients and assist with navigation through a weekly phone call after their index ED encounter for up to 45 days post ED discharge. The BH-VPN aims to improve patient outcomes through standardized approaches that leverage analytics and technology, while bridging care coordination. When a patient presents to a participating Atrium Health ED, those with a telepsychiatric consult completed on a randomized intervention day, during the hours of operation, are provided the option of participating in the BH-VPN program. A patient can choose not to receive care by a navigator post discharge.

The BH-VPN program includes the following key components: introduction to the patient follow-up process prior to ED discharge, follow-up evaluation within 72 hours by phone and weekly contact, confirmation that a follow-up visit is scheduled, where applicable confirm in-network follow-up appointments are completed with an Atrium Health provider, and placement into an appropriate case management program, if needed. There may be cases where patients are eligible to enroll in full case management programs based on their insurance and other criteria. For example, if a patient has Medicaid through Cardinal Innovations, a managed care organization providing local behavioral health care, and meets specific criteria, would no longer require navigation services. A patient's contact with the BH-VPN program ends after 45 days following ED discharge, or if there is a failure to contact, becomes enrolled with a case-management program, declines services, or the patient dies. For those patients enrolled in a case management program, then navigator will ensure the patient is in contact with case management program staff before ending contact with the patient.

This research project is a pragmatic, randomized evaluation of a quality improvement initiative which seeks to evaluate the effects of standardizing the use of a BH-VPN program among patients with a telepsychiatric consult. The outcomes evaluation of this intervention has been designed to integrate with routine care and minimize frontline staff burden by deploying an evaluation in a real-world setting.

